1.b.	Infusion-related reaction	3-4	Immediately and permanently discontinue ramucirumab
2.	Hypertension		
2.a.	Hypertension (non-life-threatening and associated with symptoms) NOTE: Hypertension should be monitored prior to each ramucirumab infusion.	3	
 • Delay ramucirumab until the hypertension is controlled with medication and is resolved to Grade 0-2. 
 ◦ If controlled with medication and resolved to Grade 0-2, then may resume ramucirumab at current dose. ◦ If NOT controlled with medication and not resolved to Grade 0-2 within a reasonable timeframe, discontinue ramucirumab at investigator's discretion.
2.b.	Uncontrolled hypertension, hypertensive crisis, or hypertensive encephalopathy	4	Immediately and permanently discontinue ramucirumab.

Dose-Modification Guidelines for Ramucirumab for Adverse Events at least Possibly Related to Ramucirumab, including Adverse Events of Special Interest (continued)

	Adverse Event NOTE: All Specific Adverse Events Listed are defined as AESIs in Section 8.2.1.1.1.	CTCAE Grade	Dose-Modification Guidelines NOTE: Dose reductions to occur as defined in Table JVDF.3.
3.	Proteinuria		
3.a.	Proteinuria = 2+ (dipstick or routine urinalysis) ^a		
 Administer ramucirumab at the current dose if clinically indicated. Obtain 24-hour urine protein results within 3 days prior to the next ramucirumab dose. 
 If urine protein is <2 g/24 h, administer ramucirumab at the patient's current dose. If urine protein is ≥2 g/24 h, modify the ramucirumab dose based on 24-hour collection. See Proteinuria ≥2 g/24 h (24-hour urine collection), Line 3.c in this table.
3.b.	Proteinuria >2+ (dipstick or routine urinalysis) ^a		
 Delay ramucirumab until urine protein returns to <2 g/24 h. Obtain 24-hour urine protein results within 3 days prior to the next ramucirumab dose. 
 If urine protein is <2 g/24 h, no further dose delay or dose reduction is required. If urine protein remains ≥2 g/24 h and is not resolved within a reasonable timeframe, discontinue ramucirumab at investigator's discretion.

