3.c.	Proteinuria ≥2 g/24 h (24-hour urine collection) ^a		
 First or second occurrence: delay ramucirumab until urine protein returns to <2 g/24 h. 
 If urine protein returns to <2 g/24 h, reduce ramucirumab dose. If urine protein remains ≥2 g/24 h and is not resolved within a reasonable timeframe, discontinue ramucirumab at investigator's discretion. Third occurrence: discontinue ramucirumab.
3.d.	Proteinuria >3 g/24 h or in the setting of nephrotic syndrome ^a		Immediately and permanently discontinue ramucirumab.
4.	Arterial thromboembolic events, venous thromboembolic events	3 or 4	Immediately and permanently discontinue ramucirumab.
5.	Bleeding/hemorrhage	3 or 4	Immediately and permanently discontinue ramucirumab.
6.	Gastrointestinal perforation		Immediately and permanently discontinue ramucirumab.

	Adverse Event NOTE: All Specific Adverse Events Listed are defined as AESIs in Section 8.2.1.1.1).	CTCAE Grade	Dose-Modification Guidelines NOTE: Dose reductions to occur as defined in Table JVDF.3.
7.	Reversible posterior leukoencephalopathy syndrome		Immediately and permanently discontinue ramucirumab.
8.	Congestive heart failure	3-4	Immediately and permanently discontinue ramucirumab.
9.	Fistula formation		Immediately and permanently discontinue ramucirumab.
10.	Impaired wound healing		
10.a.	Prior to planned surgery		Withhold ramucirumab.
10.b	After surgery		Resume ramucirumab based on clinical judgment.
10.c.	Wound-healing complications developed during study treatment		Delay ramucirumab dosing until the wound is fully healed.
11.	Liver injury/liver failure		
11.a.	Hepatic encephalopathy and/or hepatorenal syndrome resulting from liver cirrhosis		Immediately and permanently discontinue ramucirumab.
12	Hypothyroidism	2-4	Therapy with ramucirumab can be continued while treatment for the thyroid disorder is instituted.
13	Other adverse events considered at least possibly related to ramucirumab^b		
13.a	Non-life threatening and reversible	3	
May delay ramucirumab until resolved to Grade 0-1.
 
 • If resolved to Grade 0-1, may reduce ramucirumab dose. • If NOT resolved to Grade 0-1 within a reasonable timeframe, discontinue ramucirumab at investigator's discretion

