13.b	Adverse Event	4	
Permanently discontinue treatment immediately, with the exception of Grade 4 fever or Grade 4 laboratory abnormality, in which case:
 
 • First occurrence: Delay ramucirumab until resolved to Grade 0-1. 
 ◦ If resolved to Grade 0-1, may resume ramucirumab original dose at the discretion of the investigator. ◦ If NOT resolved to Grade 0-1 within a reasonable timeframe, discontinue ramucirumab at investigator's discretion. • Second occurrence: Delay ramucirumab until resolved to Grade 0-1. 
 ◦ If resolved to Grade 0-1, reduce ramucirumab dose. ◦ If NOT resolved to Grade 0-1 within a reasonable timeframe, discontinue ramucirumab at investigator's discretion.

Dose-Modification Guidelines for Ramucirumab for Adverse Events at least Possibly Related to Ramucirumab, including Adverse Events of Special Interest (concluded)

Abbreviations: AESI = adverse event of special interest; CTCAE = Common Terminology Criteria for Adverse Events; NCI = National Cancer Institute.

- a Perform urinalysis within 3 days prior to each infusion of ramucirumab. If 24-hour urine collection is also performed, the results of 24-hour urine collection should be used for clinical decision-making.
- b Patients who enter the study with symptoms or laboratory values equivalent to NCI-CTCAE Version 4.0 Grade 1-2 adverse events should not necessarily have dose delays or reductions related to the persistence or mild worsening of those symptoms or laboratory values. Grade 2 toxicities which represent clinically significant worsening of symptoms from baseline, ramucirumab dose may be delayed at the discretion of the investigator. If the toxicity is resolved to Grade 0-1, may reduce ramucirumab dose. If the toxicity is not resolved to Grade 0-1, may discontinue ramucirumab.

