6.9.1.2. Supportive Care for Ramucirumab

6.9.1.2.1. Supportive Care by Adverse Event of Special Interest

6.9.1.2.1.1. Hypertension

An increased incidence of severe hypertension (CTCAE Grade 3) has been reported in patients receiving ramucirumab compared with placebo. In most cases, hypertension was controlled using standard antihypertensive treatment. Preexisting hypertension should be controlled before starting ramucirumab treatment.

Monitoring of blood pressure is required during, and should occur prior to, ramucirumab therapy. Every attempt should be made to control blood pressure to systolic <140 mm Hg and diastolic <90 mm Hg prior to starting treatment with ramucirumab. Routine clinical and laboratory monitoring is required in patients who again develop hypertension or experience a deterioration in previous hypertension.

6.9.1.2.1.2. Proteinuria

Proteinuria is an adverse effect for all therapies targeting the VEGF/VEGF Receptor 2 pathway, including ramucirumab. In ramucirumab clinical trials, the majority of events were Grade 1 or 2. Monitoring for the development or worsening of proteinuria during ramucirumab therapy is required. Discontinue ramucirumab if the patient experiences proteinuria >3 g/24 hours or nephrotic syndrome.

6.9.1.2.1.3. Thromboembolic Events

6.9.1.2.1.3.1. Arterial Thromboembolic Events

Serious, sometimes fatal arterial thromboembolic events, including myocardial infarction, cardiac arrest, cerebrovascular accident, and cerebral ischemia, have been reported in clinical trials.

6.9.1.2.1.3.2. Venous Thromboembolic Events

Venous thromboembolic events are associated with cancer; however, the incidence of VTEs likely varies depending on the type of cancer, stage, and intensity of imaging. Additionally, VTEs have been associated with some antiangiogenic therapy, although the incidence varies depending on the type of therapy, use of concomitant chemotherapy agents, and specific disease state. VTEs have been reported from clinical studies investigating ramucirumab, particularly in the context of metastatic disease or in regions adjacent to implanted venous access devices.

6.9.1.2.1.4. Bleeding/Hemorrhage

Ramucirumab is an antiangiogenic therapy and has the potential to increase the risk of severe bleeding. Severe GI hemorrhages, including fatal events, have been reported in patients with gastric-GEJ cancer treated with ramucirumab in combination with paclitaxel.

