8.2. Safety

Investigators are responsible for monitoring the safety of patients who have entered this study and for alerting Lilly or its designee to any event that seems unusual, even if this event may be considered an unanticipated benefit to the patient.

The investigator is responsible for the appropriate medical care of patients during the study.

The investigator remains responsible for following, through an appropriate health care option, AEs that are serious, considered related to the study, or that caused the patient to discontinue before completing the study. The patient should be followed until the event is resolved or explained. Frequency of follow-up evaluation is left to the discretion of the investigator.

The timing of all safety evaluations is shown in the Time and Events Table ([Attachment 1](#)).

[Table JVDF.7](#) presents a summary of AE and SAE reporting guidelines and shows which database or storage system is used.

Table JVDF.7. Adverse Event and Serious Adverse Event Reporting Guidelines

Period	Types of AEs/SAEs to be Reported^a	Collection Database^b	Lilly Safety System
Baseline (pretreatment)	Preexisting conditions	x	X
	All AEs	x	
	SAEs related to protocol procedures	x	
Study treatment period	All AEs	x	X
	All SAEs	x	
Short-term postdiscontinuation follow-up (30 days)	All AEs	x	X
	All SAEs	x	
Long-term postdiscontinuation period			
Through post-discontinuation follow-up visit (90 days)	All SAEs	x	X
Additional long-term discontinuation follow up (every 90 days to study completion)	All SAEs related to protocol procedures or IP	x	X
Continued access period	All AEs	x	X
	All SAEs	x	
Continued access follow-up (30 days; or sooner, to occur when patient begins a new anti-cancer therapy)	All AEs	x	X
	All SAEs	x	
After the patient is no longer participating in the study (that is, no longer receiving study treatment and no longer in follow-up)	All SAEs related to protocol procedures or IP that the investigator becomes aware of		X

Abbreviations: AEs = adverse events; CRF = case report form; IP = Investigational Product (ramucirumab or pembrolizumab); SAEs = serious adverse events.

a Although not strictly adverse events, pregnancy and breastfeeding are reported as SAEs. The reporting period starts after receiving IP(s) and ends 120 days after discontinuing study treatment or 30 days following cessation of treatment if the patient initiates new anticancer therapy, whichever is earlier.

b CRF collection guidelines will be followed.

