Vital signs	X			X	X			For the first 2 ramucirumab infusions, measure blood pressure and pulse as follows: (i) within 15 minutes prior; (ii) after infusion completion; and (iii) at the end of the 1-hr post-infusion observation period. Measure blood pressure and pulse prior to each subsequent ramucirumab infusion. Measure other vital signs as clinically indicated.
AE collection; CTCAE grading	X							During short-term follow-up, all AEs/SAEs will be collected. At the 90-day long-term follow-up visit, all SAEs will be collected. Thereafter, during long-term follow-up, only SAEs that are related to study regimen or protocol procedures will be collected.

	Study Period						Notes
	Baseline (within 28 days prior to enrollment)			Treatment (21-day cycles)		Postdiscontinuation Follow-Up	
Procedure	≤28 days	≤21 days	≤7 days	Day 1	Day 8	Short-Term Follow-Up Visit (30 ±7 days)	Long-Term Follow-Up Visit (every 90 ±7 days)
Laboratory Assessment							
Hematology	X			X		X	Local only. Within 3 days prior to Day 1 of each cycle.
Chemistry	X			X		X	Local and central: Local chemistry laboratory testing will be used to determine patient eligibility and decisions for treatment. Central chemistry laboratory testing will be used for subsequent scheduled analyses. Within 3 days prior to Day 1 of each cycle.
Urinalysis	X			X		X	Local only. Within 3 days prior to Day 1 of each cycle. 24-hr urine protein analysis if urine protein is ≥2+ at baseline, >2+ during study treatment.
T3, free T4, TSH	X			X		X	Central and local as needed. At baseline, within 3 days prior to Day 1 of Cycle 3, Day 1 of Cycle 6, and every 2 cycles thereafter; and more frequently if clinically indicated.
Coagulation	X			X		X	Local only. Within 3 days prior to Day 1 of every odd-numbered cycle.
Pregnancy test			X			X	Local only. Required for women of child-bearing potential. If required per local regulations and/or institutional guidelines, testing can occur at other times during the study treatment period.

	Study Period						Notes
	Baseline (within 28 days prior to enrollment)		Treatment (21-day cycles)		Postdiscontinuation Follow-Up		
Procedure	≤28 days	≤21 days	≤7 days	Day 1	Day 8	Short-Term Follow-Up Visit (30 ±7 days)	Long-Term Follow-Up Visit (every 90 ±7 days)
Efficacy Assessment							

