Attachment 3. Protocol JVDF Clinical Laboratory Tests

Hematology-Local only	Clinical Chemistry-Local and Central^a
Hemoglobin	Serum Concentrations of:
Hematocrit	Sodium
Erythrocyte count (RBC)	Magnesium
Leukocytes (WBC)	Potassium
Absolute Neutrophil Count	Total bilirubin
Lymphocytes	Direct bilirubin (if total bilirubin is above ULN)
Monocytes	Alkaline phosphatase
Eosinophils	Alanine aminotransferase (ALT)
Basophils	Aspartate aminotransferase (AST)
Platelets	Blood urea nitrogen (BUN)
	Creatinine
	Uric acid
	Calcium
	Glucose, random
	Albumin
	Cholesterol
	Creatine kinase (CK)
	Chloride
	Total protein
	Phosphorus
	Lactate dehydrogenase (LDH)
	Pregnancy Test Urine or Serum^c-Local Only
	β-human chorionic gonadotropin (β-hCG)
Coagulation Test^d Local Only	
Prothrombin time (PT) /INR	
Partial thromboplastin time (PTT) or activated PTT (aPTT)	

Abbreviations: INR= International Normalized Ratio; RBC = red blood cells; ULN = upper limit of normal;

WBC = white blood cells.

- a. Local chemistry laboratory testing will be used to determine patient eligibility and decisions for treatment. Central chemistry laboratory testing will be used for subsequent scheduled analyses.
- b. A microscopic exam is required for abnormal results. If urinalysis indicates proteinuria $\geq 2+$ at baseline or during the treatment period, a 24 hour urine collection (to assess protein) must be obtained.
- c. Minimum sensitivity 25 IU/L or equivalent units of β-human chorionic gonadotropin (β-HCG), for women of childbearing potential (WOCBP). If urine pregnancy results cannot be confirmed as negative, a serum pregnancy test will be required.
- d. For both prothrombin time and partial thromboplastin time, the laboratory for each is selected at baseline, and should be followed during the study period.

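### Attachment 1 sets the on-treatment trigger for a 24-hour urine collection above 2+, while Attachment 3 and Table JVDF.4 also require the collection at exactly 2+

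*Protocol*

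**What the plan says.** Three places in the protocol state when a urine protein reading during treatment leads to a 24-hour collection.

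- **Attachment 1, Time and Events Table, Urinalysis row:** "24-hr urine protein analysis if urine protein is ≥2+ at baseline, >2+ during study treatment". The baseline trigger includes 2+; the on-treatment trigger does not.
- **Attachment 3, footnote b:** "If urinalysis indicates proteinuria $\geq 2+$ at baseline or during the treatment period, a 24 hour urine collection (to assess protein) must be obtained". One threshold applies to both periods, and the wording is mandatory.
- **Section 6.6.1, Table JVDF.4, line 3.a:** this row covers a reading of exactly 2+. Ramucirumab may be given at the current dose, with the instruction "Obtain 24-hour urine protein results within 3 days prior to the next ramucirumab dose". Below 2 g/24 h the current dose continues. Otherwise, "If urine protein is ≥2 g/24 h, modify the ramucirumab dose based on 24-hour collection", which leads to line 3.c.

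Table JVDF.4 then sets out what follows from the 24-hour value. Line 3.c applies at 2 g/24 h or more and begins "First or second occurrence: delay ramucirumab until urine protein returns to" below 2 g/24 h. The dose is then reduced, and a third occurrence means discontinuation. Line 3.d requires immediate and permanent discontinuation above 3 g/24 h or with nephrotic syndrome. Section 6.9.1.2.1.2 repeats this: "Discontinue ramucirumab if the patient experiences proteinuria >3 g/24 hours or nephrotic syndrome". Footnote a of the table adds that, where a 24-hour collection is also done, "the results of 24-hour urine collection should be used for clinical decision-making".

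**The concern.** For a reading of exactly 2+ during treatment, the schedule table and the other two places give opposite answers. Which one a site follows matters because Section 8.2 says "The timing of all safety evaluations is shown in the Time and Events Table", and that is the table with the narrower trigger. I found no rule saying which place takes precedence.

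The 24-hour result is the safeguard at 2+, because line 3.a does not hold the current dose. Line 3.c and the 3 g/24 h limit in line 3.d can be applied only to a 24-hour measurement. Without one, a patient at 2 g/24 h or more could go on receiving ramucirumab when the protocol requires a delay and reduction. A patient above 3 g/24 h could go on when it requires permanent discontinuation. Proteinuria is a listed ramucirumab adverse event of special interest, and safety is the study's primary objective.

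**Working it through.** The protocol states no figure to reproduce, and no formula applies to the inconsistency itself. The check is a comparison of the current text, reading by reading.

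| Reading | Attachment 1 | Attachment 3, footnote b | Table JVDF.4 | Agree? |
|---|---|---|---|---|
| Baseline, 2+ or more | Collect | Collect | Not applicable (on-treatment table) | Yes; Inclusion Criterion 6 also requires it |
| On treatment, exactly 2+ | Not called for | Collect | Collect (line 3.a) | **No** |
| On treatment, above 2+ | Collect | Collect | Collect, and delay the dose (line 3.b) | Yes |

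The disagreement is confined to one cell of the table.

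**Is it a text-reading error?** Unlikely. The Attachment 1 note uses two different symbols in one sentence, and Table JVDF.4 separately distinguishes exactly 2+ from above 2+. None of this text comes from the amendment summary.

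**Which text is out of line?** Line 3.a exists only for exactly 2+, and both of its branches depend on the 24-hour value. Under the Attachment 1 trigger it could not be carried out. In line 3.b, the cut-off above 2+ decides whether the dose is delayed, not whether urine is collected. Attachment 3 independently makes the collection mandatory. Two of the three places agree, including the one that governs dosing.

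**When is the result due?** Line 3.a needs it before the next ramucirumab dose. By the dosing days in Table JVDF.2 and the planned Phase 1b cohort sizes in Section 9.1:

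- Schedule 1 (Cohorts A, A1, A2): 15 + 25 + 25 = 65 patients. After a Day 1 dose the next is Day 8, and 8 − 1 = 7 days.
- Schedule 2 (Cohorts B, C, D, E): 15 + 25 + 25 + 25 = 90 patients. After a Day 1 dose the next is Day 22, and 22 − 1 = 21 days.
- Total: 65 + 90 = 155, matching the planned number; 65/155 = 41.9% and 90/155 = 58.1%.

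These are planned cohort sizes and scheduled intervals, before permitted delays. They show how soon the next dose follows under each schedule; they do not count patients affected. The Phase 1a patients (up to 12 evaluable for dose-limiting toxicity) are additional.

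**The case against.** The textual conflict is hard to dispute. The case on the other side concerns its weight.

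**The dosing table protects the patient.** Section 8.2 speaks of the timing of safety evaluations, not of follow-up triggered by a result. Section 6.6.1 names Table JVDF.4 as the source of the dose-modification criteria, and Attachment 1 gives no proteinuria dosing rule. A site deciding whether to dose at 2+ should reach line 3.a, which orders the test. To go wrong it would have to overlook both that line and Attachment 3. This largely stands, and it is why the risk is described as limited. It does not remove the conflict: the schedule is where sites look to see which tests to order, and Table JVDF.4 is framed as guidance for events at least possibly related to ramucirumab.

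**The note may mean something narrower.** It may refer to readings that need a 24-hour result before the current dose, which is how line 3.b treats values above 2+. It does not say that collection is barred at 2+. The reading is possible, but the note does not express it and it still conflicts with Attachment 3.

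**Repeat urinalysis limits exposure.** Footnote a of Table JVDF.4 requires urinalysis before each infusion, so a later reading above 2+ would trigger collection under all three texts. That is correct. What remains exposed is a reading that stays at 2+ while the 24-hour value is high.

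**The same row has another gap.** Footnote a covers every infusion, including Day 8 on Schedule 1, whereas the Attachment 1 row mentions only Day 1 of each cycle. This is a fair observation, but it is a separate point and does not bear on the trigger.

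**Conclusion.** The concern holds. The Attachment 1 on-treatment trigger is wrong as written: it leaves out a reading of exactly 2+, for which Attachment 3 and Table JVDF.4 both require a 24-hour collection. It should be corrected, but it is not a major defect.

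The size is one place of three and one reading category. The practical risk is a missed delay, reduction or discontinuation of ramucirumab in a patient who reads 2+ but has 2 g/24 h or more. It arises only if a site works from the schedule without consulting the dosing table. The documents give neither the frequency of 2+ readings nor the share of them with high 24-hour values, so the number of patients at risk cannot be estimated. The conclusion assumes that line 3.a and Attachment 3 express the intended rule; nothing in the documents gives a reason for a looser on-treatment trigger. Nothing here affects proteinuria grading, sample size, power or any planned analysis.

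**What to change.** In Attachment 1, Urinalysis row, replace the split trigger with a single one: 24-hr urine protein analysis if urine protein is ≥2+ at baseline or during study treatment. Leave Table JVDF.4 and Attachment 3 as they are.

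The cost is the wording of one note. No testing is added beyond what those two places already require.

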Attachment 2. Protocol JVDF Pharmacokinetic, Immunogenicity, and Biomarker Sampling Schedules

PK and immunogenicity (IK) samples will be collected for ramucirumab only, in both Phase 1a and Phase 1b portions of the study. Predose samples should be taken as close as possible to the start of first infusion, that is ramucirumab infusion, but can be drawn up to 1 hour (60 minutes) prior start of infusion, and exact clock reading should be recorded. Postdose (post end-of-infusion) samples for PK for ramucirumab should be drawn preferably at 1 hour (\pm 15 minutes) after the end of the ramucirumab infusion, and exact clock reading for the sample draw should be recorded.

Preferred time windows for each ramucirumab PK/IK sample collection are also provided in the tables in this section. While best effort should be done to draw the blood sample for ramucirumab PK/IK within the time window provided, it is more important to ensure predose sample is actually collected before the start of ramucirumab infusion and post-dose samples (post-end of infusion samples) are collected after ramucirumab infusion has actually completed. It is also equally important to record actual date and time of blood collection for ramucirumab PK/IK sample on the Requisition Form after drawing the sample (that is, do not record not planned time of collection). Sample collection for PK/IK must be from the opposite arm to that used for study drug infusion. If drug was administered via a central venous catheter, the sample collection should be from a different site.

In addition, if a patient experiences an infusion-related reaction (IRR), blood samples for anti-ramucirumab antibody and PK should be drawn. Samples will be taken at the following time points: (1) as soon as possible after the onset of the IRR, (2) at the resolution of the IRR, and (3) 30 days after the IRR.

Table ATT.2.1.

Schedule 1 (Gastric GEJ Cohort A [2nd-3rd Line] and Gastric GEJ A2 [1st Line]; and BTC Cohort A1 [2nd-3rd Line]): Pharmacokinetic (PK), Immunogenicity (IK), and Biomarker Collection Timepoints for Ramucirumab for Schedule 1 Dosing Regimen (1h Infusion Ramucirumab followed by 0.5h Infusion Pembrolizumab on Day 1 and 1h Infusion Ramucirumab on Day 8, every 3 weeks)

Visit/Cycle Day	Study Day	Sample Time (relative to start of Ram infusion) (HR:MIN) ^a	Ram PK ^f (Serum)	Ram Immunogenicity ^{e,f} (Serum)	Biomarker	
					EDTA Plasma	PBMCs
Cycle 1 Day 1 (1-hr observation period between Ram and Pem infusions)	1	0:00 hr Predose sample ^{b,d}	X (collect prior to start of first infusion)	X	X	X
		2:00 hr Postdose sample ^{c,d}	X (collect approx. 1 hr after Ram infusion ends)			
Cycle 1 Day 8 (Ram only)	8	0:00 hr Predose sample ^{b,d}	X (collect prior to start of infusion)		X	X
Cycle 2 Day 1	22	0:00 hr Predose sample ^{b,d}	X (collect prior to start of first infusion)	X	X	X
Cycle 3 Day 1	43	0:00 hr Predose sample ^{b,d}	X (collect prior to start of first infusion)		X	X
Cycle 4 Day 1	64	0:00 hr Predose sample ^{b,d}	X (collect prior to start of first infusion)	X	X	X
Cycle 5 Day 1	85	0:00 hr Predose sample ^{b,d}	X (collect prior to start of first infusion)	X	X	X
Cycle 7 Day 1	127	0:00 hr Predose sample ^{b,d}	X (collect prior to start of first infusion)	X	X	X
Cycle 7 Day 8 (Ram only)	134	0:00 hr Predose sample ^{b,d}	X (collect prior to start of infusion)		X	X
Cycle 9, Day 1	169	0:00 hr Predose ^{b,d} 2:00 hr Postdose ^{c,d}	X (collect prior to start of first infusion) X (collect approx. 1 hr after Ram infusion ends)	X	X	X
30 days Post treatment DC		Anytime ^g	X	X	X	X

Schedule 1 (Gastric GEJ Cohort A [2nd-3rd Line] and Gastric GEJ A2 [1st Line]; and BTC Cohort A1 [2nd-3rd Line]): Pharmacokinetic (PK), Immunogenicity (IK), and Biomarker Collection Timepoints for Ramucirumab for Schedule 1 Dosing Regimen (1h Infusion Ramucirumab followed by 0.5h Infusion Pembrolizumab on Day 1 and 1h Infusion Ramucirumab on Day 8, every 3 weeks) (concluded)

Note: Ram and Pem infusions are given every 3 weeks. 1-hr Ram infusion is given prior to half-hour Pem infusion. There is one-hour observation period (for infusion reactions) between Ram and Pem infusions at Cycle 1 Day 1 visit. Each cycle is a 21-day cycle.

Abbreviations: DC = Discontinuation; eCRF = electronic case report form; GEJ = gastroesophageal junction; IK = immunogenicity; IRR = infusion-related reaction; Pem = pembrolizumab; PMBC = peripheral blood mononuclear cells; PK = pharmacokinetics; Ram = ramucirumab.

- a All sample times are relative to start of first (Ram) infusion.
- b Predose sample for Ram PK, IK, and biomarkers should be preferably collected within 1 hour prior to start of first infusion, and within 15 minutes of one another.
- c Two-hour sample for Ram PK should be preferably collected at 1 hr \pm 15 minutes from the end of Ram infusion.
- d While best effort should be done to draw the blood sample for PK/IK within the time windows provided above, it is more important to ensure predose sample is actually collected before the start of first infusion and postdose samples are collected after the infusion has actually completed. It is also equally important to record ACTUAL date and time of blood collection for PK/IK sample on the Requisition Form AFTER drawing the sample and to accurately record the ACTUAL infusions start and end dates and times on the eCRF to be able to use the data for analyses. Sample collection for PK/IK must be from the opposite arm to that used for study drug infusion. If drug was administered via a central venous catheter, the sample collection should be from a different site.
- e In the event of an IRR, blood samples will be collected for both PK and IK analysis at the following time points: (i) as close as possible to the onset of the IRR, (ii) at the resolution of the IRR, and (iii) 30 days following the IRR.
- f Record ACTUAL date and time of blood collection for PK/IK sample on the Requisition Form AFTER drawing the sample.

Table ATT.2.2.

Schedule 2 (Gastric-GEJ Cancer Patients Cohort B [2nd-3rd Line], NSCLC Cohort C [2nd-4th Line], Urothelial Cancer Cohort D [2nd-4th Line]^{}, and NSCLC Cohort E [1st Line]): Pharmacokinetic (PK), Immunogenicity (IK), and Biomarker Collection Timepoints for Ramucirumab for Schedule 2 Dosing regimen (1h infusion Ramucirumab followed by 0.5h infusion Pembrolizumab on Day 1 every 3 weeks)**

Visit/Cycle Day	Study Day	Sample Time (relative to start of Ram infusion) (HR:MIN) ^a	Ram PK ^f (Serum)	Ram Immunogenicity ^{e,f} (Serum)	Biomarker Collection	
					EDTA Plasma	PBMCs
Cycle 1 Day 1 (1-hr observation period between Ram and Pem infusions)	1	0:00 hr Predose sample ^{b,d}	X (collect prior to start of first infusion)	X	X	X
		2:00 hr Postdose sample ^{c,d}	X (collect approx. 1 hr after Ram infusion ends)			
Cycle 2 Day 1	22	0:00 hr Predose sample ^{b,d}	X (collect prior to start of first infusion)	X	X	X
Cycle 3 Day 1	43	0:00 hr Predose sample ^{b,d}	X (collect prior to start of first infusion)		X	X
Cycle 4 Day 1	64	0:00 hr Predose sample ^{b,d}	X (collect prior to start of first infusion)	X	X	X
Cycle 5 Day 1	85	0:00 hr Predose sample ^{b,d}	X (collect prior to start of first infusion)	X	X	X
Cycle 7 Day 1	127	0:00 hr Predose sample ^{b,d}	X (collect prior to start of first infusion)	X	X	X
Cycle 9 Day 1	169	0:00 hr Predose ^{b,d}	X (collect prior to start of first infusion)	X	X	X
		2:00 hr Postdose ^{c,d}	X (collect approx. 1 hr after Ram infusion ends)			
30 days Post treatment DC		Anytime ^f	X	X	X	X

Schedule 2 (Gastric-GEJ Cancer Patients Cohort B [2nd-3rd Line], NSCLC Cohort C [2nd-4th Line], Urothelial Cancer Cohort D [2nd-4th Line], and NSCLC Cohort E [1st Line]): Pharmacokinetic (PK), Immunogenicity (IK), and Biomarker Collection Timepoints for Ramucirumab for Schedule 2 Dosing regimen (1h infusion Ramucirumab followed by 0.5h infusion Pembrolizumab on Day 1 every 3 weeks) (concluded)**

Notes:

Ram and Pem infusions are given Q3W. 1-hr Ram infusion is given prior to half-hour Pem infusion. There is one hour observation period (for infusion reactions) between Ram and Pem infusions at Cycle 1 Day 1 visit. Each cycle is a 21-day cycle.

Abbreviations: DC = Discontinuation; eCRF = electronic case report form; GEJ = gastroesophageal junction; IK = immunogenicity; IRR = infusion-related reaction; NSCLC = non-small cell lung cancer; Pem = pembrolizumab; PBMC = peripheral blood mononuclear cells; PK = pharmacokinetics; Ram = ramucirumab.

- ^a All sample times are relative to start of first (Ram) infusion.
- ^b Predose sample for Ram PK, IK, and biomarkers should be preferably collected within 1 hour prior to start of first infusion, and within 15 minutes of one another.
- ^c Two-hour sample for Ram PK should be preferably collected at 1 hr ±15 minutes from the end of Ram infusion.
- ^d While best effort should be done to draw the blood sample for PK/IK within the time windows provided above, it is more important to ensure predose sample is actually collected before the start of first infusion and post dose samples are collected after the infusion has actually completed. It is also equally important to record ACTUAL date and time of blood collection for PK/IK sample on the Requisition Form AFTER drawing the sample and to accurately record the ACTUAL infusions start and end dates and times on the eCRF to be able to use the data for analyses. Sample collection for PK/IK must be from the opposite arm to that used for study drug infusion. If drug was administered via a central venous catheter, the sample collection should be from a different site.
- ^e In the event of an IRR, blood samples will be collected for both PK and IK analysis at the following time points: (i) as close as possible to the onset of the IRR, (ii) at the resolution of the IRR, and (iii) 30 days following the IRR.
- ^f Record ACTUAL date and time of blood collection for PK/IK sample on the Requisition Form AFTER drawing the sample.

